The PK/PD analysis will include, but not be limited to, the determination of the relationship between exposure to siRNA, DLin-MC3-DMA and PEG₂₀₀₀-C-DMG (e.g., C_{max} and AUC) and the extent of suppression of TTR, RBP, and vitamin A (e.g., AUE, % E_{max} and E_{max}) will be explored using graphical display of data. Whenever possible the strength of the relationship correlation will be evaluated using statistical estimators (e.g. r^2 , slope, and p-value for a slope of 0). The PD and PK/PD parameters will include, but not limited to, descriptive statistics (e.g., mean, standard deviation, coefficient of variation, median, minimum, maximum, geometric mean, and geometric CV%) and also by statistical comparisons whenever possible. Other parameters may be calculated if deemed necessary. Details of the PK evaluation and analysis will be described in the PK and PK/PD analysis plan.

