7.6.15 Biomarkers of Cardiac Function

For those patients in the Cardiac subgroup, blood samples will be collected for the quantification of biomarkers of cardiac function (troponin I and NT-proBNP) prior to their first dose of study drug and approximately once every 3 months. Quantification of these biomarkers will be performed at a central laboratory.

Details of how samples will be collected, processed, and stored will be in the Study Laboratory Manual.

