9.2.8 Pharmacokinetic/Pharmacodynamic and Cardiac Subgroup Analyses

Descriptive statistics will be provided for actual values and changes from baseline in serum levels of troponin I and NT-proBNP in the subset of patients with evidence of pre-existing cardiac amyloid involvement. Results of echocardiograms will be summarized.

As part of PK/PD analysis, additional PD baseline analysis on serum TTR, RBP, and vitamin A may be conducted to include the PD data obtained during PD recovery after receiving the last dose.

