3.2. General Methods

All data listings that contain an evaluation date will contain a study day (Rel Day) relative to the first date of study medication, which is designated as Day 1. On-treatment study days will be calculated as evaluation date – first dose date +1 and pre-treatment days will be calculated as evaluation date – first dose date. For example, the day prior to study medication will be Day -1 and the second day after the first dose of study medication will be Day 2, etc.

Tabulations will be produced for appropriate demographic, baseline, clinical activity, PD, and safety parameters. For categorical variables, summary tabulations of the number and percentage of subjects within each category (with a category for missing data) of the parameter will be presented. For continuous variables, the number of subjects, mean, median, standard deviation (SD), minimum, and maximum values will be presented.

Laboratory data (including vitamin A and RBP) collected and recorded as below the limit of detection will be set equal to the lower limit of detection for the calculation of summary statistics.

As this is a Phase 2 extension study, formal statistical hypothesis testing will not be performed. Ninety-five percent confidence intervals (CIs) will be produced where indicated, and are intended to be descriptive in nature.

All data will be presented in by-subject data listings.

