3.4. Baseline Definitions

Unless otherwise noted, baseline will be defined as the study ALN-TTR02-003 Day 1 pre-dose value when non-missing, otherwise the latest value from amongst any screening or unscheduled assessments prior to dosing on Day 1 will be used (i.e., the measurement closest to and prior to dosing will be considered baseline). For PD parameters (TTR, RBP, vitamin A), baseline will be defined as the average of all records, including those from any unscheduled visits, prior to the date and time of first dose. For the mNIS+7/NIS+7 total score and individual components, grip test and 10m walk test, baseline is defined as the average of the Screening/Baseline assessments.

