4.7. Measures of Cardiac Structure and Function

For those patients in the Cardiac subgroup, cardiac structure and function will be assessed through echocardiograms as well as measurement of serum levels of the cardiac biomarkers NT-proBNP and troponin I. Quantification of these biomarkers will be performed at a central

laboratory. The assessments will be conducted prior to the first dose of study drug and approximately once every 3 months.

Descriptive statistics will be provided for actual values, changes, and percentage changes from baseline in echocardiogram parameters (including wall thickness, LV strain and other Echo parameters), serum levels of troponin I and NT-proBNP.

All echocardiogram and cardiac function biomarkers data will be presented in patient data listings.

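### The mean percentage change planned for NT-proBNP and troponin I is biased upward when nothing changes; a geometric mean ratio should be added and made the headline

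*SAP*

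**What the plan says.** The plan for these two markers has to be assembled from several sections.

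- **Measures.** SAP 4.7: "Descriptive statistics will be provided for actual values, changes, and percentage changes from baseline in echocardiogram parameters", continuing to "serum levels of troponin I and NT-proBNP". Protocol 9.2.8 is narrower: "Descriptive statistics will be provided for actual values and changes from baseline in serum levels of troponin I and NT-proBNP". Percentage change was added by the SAP.
- **Statistics.** SAP 3.2: "For continuous variables, the number of subjects, mean, median, standard deviation (SD), minimum, and maximum values will be presented". The mean is unqualified, so it is arithmetic. The median and range are shown beside it.
- **Baseline.** SAP 3.4 sets the default: "baseline will be defined as the study ALN-TTR02-003 Day 1 pre-dose value when non-missing", otherwise the latest earlier value. It then makes exceptions. One reads "For PD parameters (TTR, RBP, vitamin A), baseline will be defined as the average of all records"; another covers mNIS+7/NIS+7, grip and walk. The cardiac markers are in neither, so their baseline is one value.
- **Sampling.** Protocol 7.6.15 schedules the markers "prior to their first dose of study drug and approximately once every 3 months", that is, one pre-treatment occasion.
- **Geometric statistics.** Protocol 7.5.1 names "geometric mean, and geometric CV" for PD and PK/PD parameters. Nothing equivalent is planned for the cardiac markers.
- **Detection limit.** SAP 3.2 replaces laboratory results below the limit of detection with the limit itself.
- **Status.** Cardiac structure and function is a tertiary objective (Protocol 2.3, SAP 1.1.2.3) in a single-arm study with no hypothesis testing (SAP 3.2).

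**The concern.** Percentage changes in a positive marker are not symmetric. A doubling is +100% and a halving is -50%, so one of each averages to (100 - 50)/2 = +25%, although on a ratio scale the two cancel. When each patient's value is divided by a single noisy baseline, chance alone pushes the average percentage change above zero.

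There is no control arm in which the same artefact would appear and cancel. The same baseline value is the divisor at every three-monthly visit, so the upward shift recurs across the table and could look like a sustained rise. A reader who takes the mean percentage change at face value could see worsening where there is none, or see too small a fall where there is a real one.

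**Working it through.** The documents state no variability, subgroup size or target difference for these markers, so there is no figure of the plan's own to reproduce.

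**Inputs.** From the documents: a single baseline (SAP 3.4), and mean and median percentage change among the summaries (SAP 3.2 and 4.7). Assumed: within-patient CV of 10% to 50%, log-normal error independent between baseline and visit, and illustrative group sizes.

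**Model.** Let X be the baseline and Y the follow-up value, with the same true level. Put s² = ln(1 + CV²). Then ln(Y/X) is normal with mean 0 and variance 2s², so:

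- E[Y/X] = exp(2s²/2) = exp(s²) = 1 + CV², and the expected mean percentage change is 100 × CV².
- The median of Y/X is 1, so the median percentage change is 0.
- E[Y - X] = 0, so the mean absolute change is 0.

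**Results with no true change** (simulation of 400,000 pairs per row):

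| CV | Expected mean % change | Simulated mean % change | Simulated median % change | Simulated geometric mean ratio, as % change |
|---|---|---|---|---|
| 10% | +1% | +0.96 | -0.01 | -0.04 |
| 20% | +4% | +3.98 | -0.02 | -0.02 |
| 30% | +9% | +8.95 | -0.12 | -0.07 |
| 40% | +16% | +16.08 | +0.04 | +0.04 |
| 50% | +25% | +25.06 | -0.07 | 0.00 |

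**Small groups.** With an assumed 10 patients (60,000 simulated groups), the group mean percentage change is above zero in 65%, 71% and 80% of null samples at CV 20%, 30% and 50%. The group median is above zero in 51% and the geometric mean ratio in 50%. At CV 30% the mean percentage change averages +9.0% with a sampling SD of 15.0 points. The group median averages +1.5% and the geometric mean ratio +0.9%. This small remainder comes from expressing the result as a percentage; on the log scale the estimate is unbiased.

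**A real fall.** If the true ratio is r, the expected mean percentage change is 100 × (r(1 + CV²) - 1).

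- True 10% fall, CV 30%: 0.9 × 1.09 - 1 = -1.9%.
- True 10% fall, CV 40%: 0.9 × 1.16 - 1 = +4.4%.
- True 20% fall, CV 50%: 0.8 × 1.25 - 1 = 0%.

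**Correlated errors.** If the log errors have correlation ρ, the bias becomes (1 + CV²)^(1-ρ) - 1. At CV 30% and ρ = 0.5 (assumed) it is √1.09 - 1 = 4.4%, about half of 9%.

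**A second baseline sample.** Dividing by the arithmetic average of two baseline samples only about halves the bias: 2.0%, 4.5% and 12.4% at CV 20%, 30% and 50%. It also moves the median percentage change below zero (-2.2% at CV 30%).

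**The case against.** The strongest reply is that the mean percentage change is one column among several. SAP 3.2 already requires the median, minimum and maximum; SAP 4.7 also gives actual values and absolute changes; every patient is listed. Under the model used here, the median percentage change and the mean absolute change are centred on zero. A reader might infer that the SAP judges these markers by the mean percentage change alone, or that the cardiac objective rests on it. The documents do not support that: the objective also covers echocardiograms, and no test or decision rule uses this table. This part of the objection stands and limits the point.

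The second reply is that the size is assumed. That also stands. At CV 10% to 20% the bias is 1 to 4 points, and correlated errors reduce it. Even at CV 30% with 10 patients it is smaller than the sampling SD of the mean. A reader might infer a large artefact or a false claim of benefit. Neither follows: the documents give no CV, and the direction is toward apparent worsening.

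The third reply is that a ratio has weaknesses too. Replacing results below detection with the limit can distort a troponin I ratio. This is fair, and is a reason to report how often it happens.

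What the objection does not remove is that a biased statistic will sit beside better ones, with nothing in the SAP to say which to read.

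**Conclusion.** The point holds in a limited form. SAP 4.7, read with SAP 3.2 and 3.4, will report for NT-proBNP and troponin I a mean percentage change whose expectation under no change is about CV² rather than zero: +1% to +25% over an assumed CV of 10% to 50%. This rests on independent log-normal error and a single baseline. Substitution at the detection limit would alter the figure for troponin I. The consequence is confined to how one tertiary, descriptive table is read: apparent worsening, or a real fall understated. It is an improvement to presentation that costs little; it does not invalidate the cardiac analysis.

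**What to change.** In SAP 4.7, for NT-proBNP and troponin I:

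- Add the geometric mean of the visit-to-baseline ratio at each visit, from the mean of log(visit/baseline), with a 95% CI labelled descriptive. SAP 3.2 already allows descriptive intervals.
- State that this ratio, with the median and range already planned, is the headline summary. The mean percentage change may stay in the table but is not to be interpreted.
- Report at each visit, including baseline, how many troponin I values were set to the detection limit, since the substitution also affects the ratio.

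No new data are needed. The cost is a few lines of SAP text and a small amount of extra programming.

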4.8. Anti-Drug Antibody

Anti-drug antibody data will be presented in a patient data listing.

5. CHANGES TO PLANNED ANALYSES

The changes to planned analyses include the following:

7. QUESTIONNAIRE/SCORING APPENDICES

In questionnaires, if multiple responses are provided to a single-response question, the question is deemed as missing.

7.1. Modified Neuropathy Impairment Score (mNIS+7) and Original Neuropathy Impairment Score + 7 Nerve Tests (NIS+7)

Note: the mNIS+7 and NIS+7 measurements are conducted in duplicate per timepoint. The average of two complete duplicate values will be reported, except in cases of missing or partially missing data as described below.

Assessment Tool	Total Points	Components (maximum points)
Modified NIS+7	304	
 • NIS-W: Weakness (192) • NIS-R: Reflexes (20) • Quantitative sensory testing by body surface area including touch pressure (TP) and heat as pain (HP): QST-BSA_{TP+HP5} (80) • $\sum 5$ nerve conduction studies (10) 
 • Ulnar compound muscle action potential (ulnar CMAP) • Ulnar sensory nerve action potential (ulnar SNAP) • Sural sensory nerve action potential (sural SNAP) • Tibial compound muscle action potential (tibial CMAP) • Peroneal compound muscle action potential (peroneal CMAP) • Postural blood pressure (BP) (2)
NIS+7	270	
 • NIS-W: Weakness (192) • NIS-R: Reflexes (20) • NIS-S: Sensation (32) • $\sum 7$ Nerve tests 
 • 5 Nerve conduction studies $\sum 5$ (18.6) 
 • Peroneal compound muscle action potential (peroneal CMAP) • Peroneal motor nerve conduction velocity (peroneal MNCV) • Peroneal motor nerve distal latency (peroneal MNDL) • Tibial motor DL • Sural sensory nerve action potential (sural SNAP) • Vibration detection threshold (VDT) (3.72) • Heart rate response to deep breathing (HRdb) (3.72)

7.1.1. Modified Neuropathy Impairment Score (mNIS+7)

There are five components within mNIS+7 total score including NIS-W, NIS-R, QST, $\Sigma 5$ NC, and postural BP, as described in details below:

Figure 1 consists of five panels arranged vertically, each showing a 2D interface. The background is black. A white horizontal band is centered in each panel. The interface is represented by a red line. In the first panel, the red line is a single horizontal segment. In the second panel, the red line is a single horizontal segment. In the third panel, the red line is a single horizontal segment. In the fourth panel, the red line is a single horizontal segment. In the fifth panel, the red line is a single horizontal segment.

If at least one value at a timepoint and (replicate) assessment is missing then do the following:

1. **What is the primary purpose of the proposed legislation?**

7.1.2. Original Neuropathy Impairment Score (NIS+7)

[figure not shown]
7.1.3. NIS Total Score

[figure not shown]

[figure not shown]
[figure not shown]
7.1.4. Algorithms for Setting Normal Deviates and Points

A 10x10 grid of black bars with red outlines. The bars are arranged in a sparse pattern, with most cells being white. The bars are of varying widths and heights, creating a textured appearance. The red outlines are thick and clearly define the boundaries of each bar. The overall pattern is irregular and lacks a clear, repeating structure.

7.2. Euro Quality of Life-5-Dimension 5-Level (EQ-5D-5L)

Each of the 5 dimensions (Mobility, Self-Care, Usual Activities, Pain/Discomfort, Anxiety/Depression) is scored on a 5-point Likert scale from 1 (“I have no problems/pain/anxiety”) to 5 (“I am unable to…”, “I have extreme anxiety/depression”).

The five scores are concatenated together (in the order of Mobility, Self-Care, Usual Activities, Pain/Discomfort, Anxiety/Depression) to create an EQ-5D-5L profile (e.g., 11111, 55555). The profile is then used to obtain an index value using the United States value set. The index values range from -0.109, associated with a profile of 55555, to 1.0, associated with a profile of 11111. Smaller index values indicate greater impairment.

Missing values are handled as follows:

- Missing items are coded as “9” in creating patient profiles.
- The index value is deemed as missing when responses are missing for 1 or more of the five dimensions.

If the entire instrument is missing, the EQ-5D-5L index value is considered as missing.

7.3. Rasch-Built Overall Disability Scale (R-ODS)

The R-ODS consists of 24 items scored on a scale of 0 (unable to perform), 1 (able to perform, but with difficulty) or 2 (able to perform without difficulty). A total score will be calculated as the average of all non-missing items multiplied by 24 if at least 90% of the items are non-missing. The total score will be deemed as missing if more than 10% of the items (3 or more items) are missing.

7.4. Composite Autonomic Symptom Score (COMPASS-31)

The COMPASS-31 questionnaire comprises 6 domains: Orthostatic intolerance, Vasomotor, Secretomotor, Gastrointestinal, Bladder, and Pupillomotor. Within each domain, individual questions are scored as follows: Simple yes or no questions are scored as 0 points for no and 1 point for yes. Questions about a specific site of symptoms or symptoms under specific circumstances are scored as 0 if not present and as 1 if present for each site or circumstance. All questions regarding the frequency of symptoms are scored as 0 points for rarely or never, 1 point for occasionally or sometimes, 2 points for frequently or “a lot of the time,” and 3 points for almost always or constantly. All questions regarding the severity of symptoms are scored as 1 point for mild, 2 points for moderate, and 3 points for severe. Questions assessing the time course of a symptom are scored 0 points for responses such as “gotten somewhat better,” “gotten much better,” “completely gone,” and “I have not had any of these symptoms,” 1 point for “stayed about the same,” 2 points for “gotten somewhat worse,” and 3 points for “gotten much worse.” The scores for changes in bodily functions depend on the individual question asked. For example, “I get full a lot more quickly than I used to when eating a meal” is scored 2 points and “I get full a lot less quickly than I used to” is scored 0 points, while the answer “I sweat much more than I used to” is given 1 point and “I sweat much less than I used to” is scored 2 points.
